11.5 Physical Examinations

Physical examination abnormalities will be presented in subject data listings. The following body systems will be assessed:

- General appearance
- Head, Neck, Thyroid
- Ears, Eyes, Nose, Throat, Mouth
- Chest (excluding breasts)
- Respiratory
- Cardiovascular
- Lymph nodes
- Abdomen
- Skin, Hair, Nails
- Musculoskeletal
- Neurological
- Other

11.6 Columbia-Suicide Severity Rating Scale (C-SSRS)

The Columbia-Suicide Severity Rating Scale measures four elements: the severity of ideation, the intensity of ideation, behavior and lethality. The C-SSRS consists of 10 categories, with a binary response option (yes/no). Categories include:

1. Wish to be Dead
2. Non-specific Active Suicidal Thoughts
3. Active Suicidal Ideation with Any Methods (Not Plan) without Intent to Act
4. Active Suicidal Ideation with Some Intent to Act, without Specific Plan
5. Active Suicidal Ideation with Specific Plan and Intent
6. Preparatory Acts or Behavior
7. Aborted Attempt
8. Interrupted Attempt
9. Actual Attempt (nonfatal)
10. Completed Suicide.

The C-SSRS will be completed at Screening(Baseline), Day 7, Day 14, and Follow-Up. The outcome of the C-SSRS is a numerical score obtained from the 10 categories stated above.

In addition, three C-SSRS composite indicator variables will be calculated as follows:

(1) C-SSRS suicidal ideation indicator

A composite indicator of C-SSRS suicidal ideation (Items 1-5 above) will be calculated as:

- IF the response to any one of the five suicidal ideation questions is “Yes”, THEN set the suicidal ideation indicator equal to 1.
- OTHERWISE, set the suicidal ideation indicator equal to 0.

(2) C-SSRS suicidal behavior indicator

A composite indicator of C-SSRS behavior ideation (Items 6-10 above) will be calculated as:

- IF the response to any one of the five suicidal behavior questions is “Yes”, THEN set the suicidal behavior indicator equal to 1.
- OTHERWISE, set the suicidal behavior indicator equal to 0.

(3) C-SSRS suicidal ideation or behavior indicator

A composite indicator of C-SSRS suicidal ideation or behavior will be calculated as:

- IF the response to any one of the 5 suicidal ideation questions or any of the 5 suicidal behavior questions is “Yes”, THEN set the suicidal ideation or behavior indicator equal to 1.
- OTHERWISE, set the suicidal ideation or behavior indicator equal to 0.

The C-SSRS will be evaluated in the Safety Set based on methods described by Nilsson. The number and percentage of subjects with any suicidal ideation and/or suicidal behavior following the first dose of study drug will be tabulated.

For the composite endpoint of suicidal ideation, the number and percent of subjects who experience any one of the five suicidal ideation events at least once during treatment through follow-up will be tabulated.

For the composite endpoint of suicidal behavior, the number and percent of subjects who experience any one of the five suicidal behavior events at least once during treatment through follow-up will be tabulated.

For the composite endpoint of suicidal ideation or behavior, the number and percent of subjects who experience any one of the ten suicidal ideation or behavior events at least once during treatment through follow-up will be tabulated.

Results from the C-SSRS will be presented in a listing.

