2.3. Secondary Endpoints

The secondary endpoints will compare the effect of CST-2032 administered with CST-107 versus placebo on the following:

- Cognitive tasks in Cambridge Neuropsychological Test Automated Battery (CANTAB) and other cognitive measures:
 - Reaction Time (RTI)— attention
 - Verbal Recognition Memory (VRM) – episodic memory (verbal stimuli)
 - Adaptive Tracking Task (ATT) – visuospatial with strong attentional demand
 - Paired Associates Learning (PAL) – episodic memory (visual stimuli)
 - Delayed Verbal Recall— episodic memory (verbal stimuli)
 - Stop Signal Task (SST) – response inhibition (impulsivity), an aspect of executive function
 - Phonological verbal fluency (pVFT)
 - Digit symbol substitution test (DSST)
 - Color Trails Test (select sites only)
- Facial expression recognition task (FERT)
- Geriatric Depression Scale – 30 questions (GDS-30)
- Conners Adult Attention Deficit Hyperactivity Disorder Scale (ADHD) Rating Scale, short form, self-report (CAARS)
- Starkstein Apathy scale short form (SAS-6)
- Alzheimer's Disease Cooperative Study-Clinical Global Impression of Change (ADCS-CGIC)
- Suicidal ideation using the Columbia Suicide Severity Rating Scale (C-SSRS).
- Plasma pharmacokinetics (PK) parameters of CST-2032 and CST-107 (including C_{max} , t_{max} , AUC_t , $t_{1/2}$).

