 6. C-SSRS

Subjects with a positive drug or alcohol screen at Screening will be rechecked once and if positive, the subject will be excluded from participation in the study. The drug and/or alcohol screen tests may be repeated per Investigator clinical judgement.

Subjects who are eligible for study participation will be scheduled to return to the clinic for the start of Treatment Period 1.

5.1.2. Day -1, one day before start of dosing of Study Drug in Treatment Periods 1 and 2

The following procedures will be performed, and assessments/measurements recorded:

- Review of inclusion/exclusion criteria (Treatment Period 1 only)
- Assessment of concomitant medications
- Vital signs (BP, HR, respiration rate, and oral/tympanic temperature); for assessments of orthostatic changes, BP and HR are obtained: a) after rest in a supine position for at least 5 minutes, and b) 1 minute after standing
- 3 sets of triplicate ECG measures (i.e., 9 ECGs) prior to dosing with study drug to thoroughly establish a baseline obtained after subject has rested in supine position for at least 5 minutes; the time between each set of 3 ECGs should be \leq 5 minutes
- Alcohol breath test prior to dosing CST-107 or matching placebo
- Serum or urine pregnancy test (per standard site practice) prior to dosing CST-107 or matching placebo for females of childbearing potential; positive urine pregnancy result to be confirmed by serum test

The following procedures will be administered (prior to dosing CST-107) at approximately the same time of day (\pm 1 hour) and under approximately the same food status as planned for the tests on Days 1, 7, and 14:

- FERT
- pVFT
- DSST
- CANTAB
- Color Trails Test (select sites only), administered after CANTAB
- SAS-6
- CAARS
- GDS-30
- C-SSRS in Treatment Period 2 only

Obtain the randomization number and the Days 1-7 blister card/bottle numbers for study drug (CST-2032+CST-107 or matching placebos) from the IWRS – do not dispense blister card/bottle to the subject

Remove one CST-107 or matching placebo tablet from the bottle or the Day 10 well on the blister card and administer the dose to the subject after completion of all scheduled assessments

5.1.3. Day 1, Treatment Periods 1 and 2

The following procedures will be performed, and assessments/measurements recorded:

- Assessment of concomitant medications

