8.8. Analysis of Secondary Endpoints

Differences between CST-2032+CST-107 and placebo in performance in cognitive tasks will be assessed using the FAS. For continuous endpoints, the difference is defined as CST-2032+CST-107 minus placebo except as defined in the SAP (e.g., for certain CANTAB test [PAL, RTI, and SSRT]). Comparisons may be made using a mixed model with factors for disease criteria, treatment, treatment sequence, subject nested in sequence (as a random effect), period, and baseline values as appropriate. Comparisons between treatments may also be compared using the paired t-test and/or nonparametric tests where appropriate and as specified in the SAP. These analyses will be conducted for all subjects in the study and also for each disease subset (PD/AD).

Secondary endpoints related to cognition, physiological symptoms, mood and will be summarized by disease criteria, treatment, treatment sequence and overall using the FAS. Select summaries may be repeated in the PPS. Comparisons between treatments will be performed similarly for all secondary endpoints. All data will be listed.

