3 STUDY OBJECTIVES AND ENDPOINTS

Objectives	Endpoints
Primary The primary objective of this study is to evaluate the safety and tolerability of CST-2032 when combined with CST-107.	The primary endpoint is safety and tolerability of CST-2032 including adverse event rates (AEs), serious adverse event rates (SAEs), study discontinuation rates, electrocardiograms (ECGs), vital signs, and laboratory safety observations.
Secondary The secondary objectives of this study will evaluate the effects of CST-2032 when combined with CST-107 versus placebo on the following measures: 
1. Cognition2. Mood3. Attention Deficit4. Apathy5. Overall clinical improvement6. PK	The secondary endpoints will compare the effect of CST-2032 administered with CST-107 versus placebo on the following: 
• Cognitive tasks in the Cambridge Neuropsychological Test Automated Battery (CANTAB) and other cognitive measures:
○ Reaction Time (RT) – attention○ Verbal Recognition Memory (VRM) – episodic memory (verbal stimuli)○ Adaptive Tracking Task (ATT) – visuospatial with strong attentional demand○ Paired Associates Learning (PAL) – episodic memory (visual stimuli)

	
○ Delayed Verbal Recall – episodic memory (verbal stimuli)○ Stop Signal Task (SST) – response inhibition (impulsivity), an aspect of executive function○ Phonological verbal fluency (pVFT)○ Digit symbol substitution test (DSST)○ Color Trails Test (select sites only)● Facial expression recognition task (FERT).● Geriatric Depression Scale – 30 questions (GDS-30).● Conners Adult Attention Deficit Hyperactivity Disorder (ADHD) Rating Scale, short form, self-report (CAARS).● Starkstein Apathy scale short form (SAS-6).● Alzheimer's Disease Cooperative Study-Clinical Global Impression of Change (ADCS-CGIC).● Suicidal ideation using the Columbia Suicide Severity Rating Scale (C-SSRS).● Plasma pharmacokinetics (PK) parameters of CST-2032 and CST-107 (including C_{max}, t_{max}, AUC_t, $t_{1/2}$).
--	--

Exploratory

The exploratory objectives are:

- To evaluate whether baseline disease characteristics impact response to treatment.
- To characterize the effects of treatment on neurodegenerative biomarkers in the blood such as neurofilament light chain, total and phosphorylated tau protein, and amyloid- β (A β) peptides may also be measured.

The following exploratory endpoints may be undertaken to evaluate:

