6 DATA ANALYSIS CONSIDERATIONS

6.1 General Data Handling

All analyses will be conducted based on SAS 9.4 or higher.

Study data will be recorded in eCRFs for all screened and randomized patients. The EDC vendor for this study is MedNet Solutions.

Unless otherwise stated, all listings will be sorted by disease type, treatment sequence, subject number, and assessment date (and time, if available).

Unless stated otherwise, continuous data will be summarized by disease type, treatment sequence, and overall using n, mean, median, standard deviation (SD), minimum value, and maximum value.

Unless stated otherwise, categorical data will be summarized by disease type, treatment sequence, and overall using frequency counts and percentages. Where applicable, 95% confidence intervals (CIs) will be provided. Unless otherwise stated, the denominator of percentages will be the number of participants in the population/treatment arm or the number with non-missing data.

- The number of missing values will be presented as a separate category with no percentage, but only if one or more subjects are missing data.
- Counts of zero will be presented without percentages.

Relative to the number of digits after the decimal in the raw data, summary statistics will have the following number of digits after the decimal:

- Minimum and Maximum: same number of significant digits as the raw data
- Mean and Median: one additional decimal place to that reported for Minimum and Maximum
- SD or Standard Error (SE): two additional decimal places than the Minimum and Maximum
- Percentages: reported to one decimal place
- P-values will be reported to four decimal places. If the value is below 0.0001 it will be noted as < 0.0001; if the value is above 0.9999 it will be noted as > 0.9999.

Unless otherwise noted, statistical inference will be based on a 5% significance level (i.e. 95% confidence intervals will be produced).

All data up to the time of study completion/withdrawal from the study will be included in the analysis, regardless of duration of treatment.

Numbering for data displays will be based on ICH E3.

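### SAP 11.6 counts C-SSRS events once per subject over both crossover periods with no rule assigning them to a treatment, so the planned table would not show the stated active-versus-placebo comparison

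*SAP*

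**What the plan says.** SAP 3 introduces the secondary endpoints with the words "The secondary endpoints will compare the effect of CST-2032 administered with CST-107 versus placebo on the following", and its list includes suicidal ideation on the C-SSRS, as does Protocol 2.3. Protocol 8.8 adds: "Comparisons between treatments will be performed similarly for all secondary endpoints". The C-SSRS has no entry in SAP 9.2, so SAP 11.6 is the only text that describes its tabulation.

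SAP 11.6 forms three yes/no indicators: ideation (items 1-5), behaviour (items 6-10), and either. It uses the Safety Set. The general rule is: "The number and percentage of subjects with any suicidal ideation and/or suicidal behavior following the first dose of study drug will be tabulated". The ideation composite covers subjects who "experience any one of the five suicidal ideation events at least once during treatment through follow-up will be tabulated", and the other two composites follow the same pattern. No treatment, period or comparison with a pre-dose response is named. The layout default in SAP 6.1, which applies unless another is stated, is that "categorical data will be summarized by disease type, treatment sequence, and overall using frequency counts and percentages".

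On visits, SAP 11.6 says: "The C-SSRS will be completed at Screening(Baseline), Day 7, Day 14, and Follow-Up". Protocol 5.1.2 also schedules, on Day -1 before the CST-107 dose, "C-SSRS in Treatment Period 2 only". SAP Appendix 2 includes that visit and additionally marks a Day 1 C-SSRS. The protocol's Schedule of Events, Protocol 5.1.3 and SAP 11.6 do not have a Day 1 C-SSRS. Protocol 8.10 plans only to list C-SSRS results.

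**The concern.** In a crossover, a count of subjects with an event at any time after first dose mixes time on active, time on placebo and the washout. Splitting that count by sequence does not separate the treatments, because each sequence contains both. A table built this way would leave unanswered the question set for the endpoint, whether ideation is more frequent on CST-2032 plus CST-107 than on placebo.

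A second problem concerns the starting point. Exclusion criterion 15 bars only a Yes on ideation items 4 or 5 in the 3 months before Screening, so a subject with items 1-3 present can enter. If the same ideation continues, SAP 11.6 counts it as a post-dose event. The Period 2 Day -1 response falls after the first dose of the study but before any Period 2 dose. Under the wording of SAP 11.6 a Yes there counts as an event, with no treatment to which it belongs.

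**Working it through.** The plan gives no figure to reproduce. The sample size of about 60 rests on practical considerations (SAP 4.3), and neither document states a C-SSRS rate.

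**Step 1: where the SAP states attribution to treatment.**

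| Data | Section | Rule |
|---|---|---|
| Adverse events | SAP 11.1 | By period; washout to the Period 1 treatment, after Period 2 to the Period 2 treatment |
| Vital signs | SAP 11.3 | Treatment at the time of collection |
| Exposure | SAP 8.7 | Treatment taken at the time of collection |
| Efficacy data | SAP 9 | Treatment assigned at the time of collection |
| C-SSRS | SAP 11.6 | None |

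**Step 2: what the planned count can show.** Let p be the probability of at least one Yes in a placebo period and a the same for an active period. Assume independent periods, no period or carryover effect, and all 60 subjects completing both periods, 30 per sequence (1:1 allocation, SAP 4.2). Then, in either sequence,

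P(any event over the study) = 1 - (1 - p)(1 - a).

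The expression is symmetric in p and a, so exchanging the two rates does not change it. The rates below are assumptions for illustration:

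| Placebo p | Active a | Any event, each sequence | Expected of 60 overall | By treatment: active / placebo, of 60 |
|---|---|---|---|---|
| 2% | 2% | 3.96% | 2.38 | 1.2 / 1.2 |
| 2% | 10% | 11.8% | 7.08 | 6.0 / 1.2 |
| 5% | 5% | 9.75% | 5.85 | 3.0 / 3.0 |
| 5% | 15% | 19.25% | 11.55 | 9.0 / 3.0 |
| 15% | 5% | 19.25% | 11.55 | 3.0 / 9.0 |
| 5% | 20% | 24.0% | 14.4 | 12.0 / 3.0 |

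For the fourth row: 1 - 0.95 × 0.85 = 1 - 0.8075 = 0.1925, and 60 × 0.1925 = 11.55. The fourth and fifth rows have opposite treatment effects and the same planned table. A split by treatment at the time of assessment tells them apart.

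**Step 3: whether the data for that split are scheduled.** Following the SAP 11.1 convention, the Period 1 treatment has Day 7, Day 14 and Period 2 Day -1. The Period 2 treatment has Day 7, Day 14 and End of Study. That is three post-dose assessments per treatment period. Each period also has a pre-dose assessment, Screening for Period 1 and Day -1 for Period 2. No added visit is needed.

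**The case against.** The best reply is that the documents, read together, already point to a by-treatment display. SAP 5 reports the Safety Set as treated. The protocol synopsis and Protocol 8.5 and 8.7 present safety by treatment. SAP 7.1 gives each period its own treatment start date, so the first dose in SAP 11.6 could be read as the first dose of each period. SAP 9 presents efficacy data by treatment at the time of collection. Layout wording is sparse elsewhere in SAP 11 too, so silence in 11.6 need not mean a table by sequence.

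This stands in part. It shows that a by-treatment table may have been intended. It does not supply the rule. A completer has received both treatments, so reporting as treated does not say which column holds a once-per-subject event. A window that opens at Period 1 dosing and runs through follow-up still takes in Period 2. The time-of-collection convention gives no column for Period 2 Day -1 or End of Study, when no treatment is being taken.

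SAP 11.6 also cites a scoring and analysis guide, which is not part of the documents. Whether it supplies a baseline comparison cannot be checked here. SAP 11.6 does label Screening as baseline, but its counting rules make no use of it.

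A reader might infer that the comparison cannot be made at all, or that C-SSRS data have no link to treatment. The documents do not support either. Visits occur in both periods, all results are listed, and SAP 5 gives a general treatment-received link. Ideation recorded as an adverse event would also be attributed by period under SAP 11.1.

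**Conclusion.** Wrong as written, with modest impact. SAP 11.6 has no rule that assigns a C-SSRS response to a treatment or period, and under the SAP 6.1 default its table would not show the comparison stated in SAP 3 and Protocol 2.3 and 8.8. It would also count ideation on items 1-3 that was present before dosing.

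The finding that the table has the same expected value whichever treatment carries the higher rate rests on the Step 2 assumptions of independent periods, no period or carryover effect and full completion. The rates there are assumed, so the counts illustrate the mechanism and do not predict a result. Early withdrawals would make the sequences differ somewhat, but that difference would not be a clean treatment contrast.

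The impact is limited because the comparison could be rebuilt from planned visits and the listing. Testing is also informal (SAP 6.4), the study is not powered for this endpoint, and events are probably few.

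**What to change.** In SAP 11.6, before unblinding:

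- Tabulate each of the three indicators once per subject per treatment, by treatment at the time of assessment.
- Extend the SAP 11.1 convention to the C-SSRS: washout responses, including Period 2 Day -1, go to the Period 1 treatment, and End of Study goes to the Period 2 treatment.
- Report new or worsened ideation or behaviour against a stated reference for each period, Screening for Period 1 and Day -1 for Period 2. Note that the two references differ in timing: Screening may fall anywhere from Day -28 to Day -2.
- Keep the any-event count as a supplementary display.
- Add Period 2 Day -1 to the visit list in 11.6, and reconcile the Day 1 C-SSRS in SAP Appendix 2 with the protocol schedule.

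Neither document states the recall window of the C-SSRS form, so these rules work from the date of assessment and do not depend on it. The cost is SAP wording and one reprogrammed table, with no new data.

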- CANTAB, pVFT and DSST to be administered on Days 1, 7 and 14 of each treatment period:
 - 3 ± 0.5 hours after administration of study drug. Tests should be conducted at approximately the same time of day (± 1 hour) and under the same food status on Days -1, 1, 7 and 14.

15 SAS-6, CAARS, and GDS-30 are per subject self-report. These tests will be administered at the following timepoints in each treatment period:

- Day -1: Prior to administration of CST-107 or matching placebo
- Day 1: at least 2 hours after dosing of study drug,
- Day 14: at least 2 hours after dosing of study drug.

16 C-SSRS not completed on Day -1 during Treatment Period 1.

17 The ADCS-CGIC will be administered at the following timepoints in each treatment period:

- Screening
- Day 14: at least 3 hours after dosing of study drug.

18 On Day -1 only, CST-107 or matching placebo is to be administered upon completion of all scheduled study assessments. On all other dosing days, study drugs (CST-2032+CST-107 or matching placebos) are to be co-administered. On Days -1, 1, 7 and 14 the study drugs are administered in the clinic.

19 On Day 1, safety labs will be collected pre-dose and approximately 4 hours post-dose (chemistry only at 4 hours post-dose).

20 On Days 7 and 14, safety labs will be collected approximately 4 hours post-dose.

21 Inclusion/exclusion criteria not re-assessed on Day -1 of Treatment Period 2.

LIST OF ABBREVIATIONS

Abbreviation	Definition
ADCS-CGIC	Alzheimer's Disease Cooperative Study-Clinical Global Impression of Change
APOE4	Apolipoprotein E4
β-AR	Beta-adrenoceptor
β-hCG	Beta human chorionic gonadotropin
AD	Alzheimer's Disease
AE	Adverse event
ADHD	Attention Deficit/Hyperactivity Disorder
AS	Apathy scale
ASL MRI	Arterial spin labelling magnetic resonance imaging
ATT	Adaptive tracking test
AUC _{inf}	Area under the drug concentration-time curve from time zero to infinity
AUC _t	Area under the drug concentration-time curve from time zero to time t
BMI	Body mass index
BP	Blood pressure
CAARS	Connors Adult Attention Deficit/Hyperactivity Disorder Scale – short form, self-report
cAMP	cyclic adenosine monophosphate
CANTAB	Cambridge Neuropsychological Test Automated Battery
CBF	Cerebral blood flow
cGCP	Current Good Clinical Practice
CLIN-002	CST103/CST107/CST109-CLIN-002
CLIN-007	CST2032-CLIN-007
Cmax	Maximum concentration
CNR	Contrast-to-noise ratio
CNS	Central nervous system
CRF	Case report form
CST-107	Nadolol
DSMB	Data and Safety Monitoring Board

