7. Any current clinically significant medical condition or disease as determined by medical history, physical examination, 12-lead electrocardiogram (ECG) and clinical laboratory assessments conducted that, in the view of the Principal Investigator, will interfere with participation in the study or interpretation of results.
8. Clinically significant abnormalities of 12-lead ECG (as determined by a central reader), including QTcF > 440 ms, for males and females, and/or HR < 50 beats per minute, or evidence of bundle branch blocks, as indicated on the Mean ECG Analysis Report during the screening period.
9. A calculated creatinine clearance of \leq 60 mL/min according to the Cockcroft-Gault equation.
10. Current use of any prohibited prescription medication, over-the-counter medication, or herbal supplements including green tea products (refer to [Section 5.4](#)) during Screening or throughout study, unless approved by both the Investigator and the Sponsor Medical Monitor.

11. Prior and/or concurrent treatment with any investigational drug \leq 90 days prior to dosing (Day -1), or \leq 5 half-lives of the drug (whichever is longer), or current enrollment in any other study treatment or disease study, except for observational studies.
12. Prior and/or concurrent treatment with any β -AR agonists or β -AR blockers (includes oral meds, IV or inhaled) or any meds that impact adrenergic signaling within the last month prior to Screening. Subjects maybe on stable doses of serotonin-selective reuptake inhibitor (SSRI) antidepressants but are prohibited to be on serotonin-noradrenaline reuptake inhibitors (SNRIs), or tricyclic antidepressants (TCAs), or any treatment for ADHD including noradrenaline reuptake inhibitors (NRIs), or amphetamines within the last month prior to Screening.
13. A history of heart failure, sinus bradycardia, second- or third-degree heart block, hypokalemia, attack of unconsciousness possibly associated with torsades de pointes (TdP) or family history of Long QT Syndrome.
14. Known or suspected alcohol or substance abuse within the past 12 months and/or positive test for alcohol or drugs of abuse at Screening or Day -1.
15. Suicidal ideation with actual intent or plan ("Yes" answer on the C-SSRS ideation items 4 or 5) within 3 months prior to study Screening.

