7.4 Missing Data and Data Imputation Rules

All attempts will be made by the Data Management team to ensure completeness of data. Generally, missing data will not be imputed, and will be presented as collected in the study database.

In cases where adverse event (AE) or medication dates are missing, the imputation methods described in Appendix 1 will be used to determine flags for treatment-emergent events, and concomitant medications.

Other missing data methods will be proposed within the respective analysis section, as needed.

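### SAP 11.6 counts any post-dose C-SSRS Yes without using the baseline it names, so persisting entry ideation cannot be separated from new or worsened ideation in the tables

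*SAP*

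**What the plan says.** Protocol 2.3 lists suicidal ideation on the C-SSRS among the secondary endpoints that compare active treatment with placebo. Protocol 8.10 plans only a listing. SAP 11.6 goes further and tabulates the scale in the Safety Set.

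- **Visits and baseline (SAP 11.6):** "The C-SSRS will be completed at Screening(Baseline), Day 7, Day 14, and Follow-Up".
- **Overall count (SAP 11.6):** "The number and percentage of subjects with any suicidal ideation and/or suicidal behavior following the first dose of study drug will be tabulated".
- **Composite counts (SAP 11.6):** subjects "who experience any one of the five suicidal ideation events at least once during treatment through follow-up will be tabulated" and, for behavior, subjects "who experience any one of the five suicidal behavior events at least once during treatment through follow-up will be tabulated". A third table combines the two.
- **Indicator rule (SAP 11.6):** any Yes gives 1; then "OTHERWISE, set the suicidal ideation indicator equal to 0". The behavior and combined indicators end in the same way.
- **Missing data (SAP 7.4):** "Generally, missing data will not be imputed, and will be presented as collected in the study database". For percentages, SAP 6.1 allows either the whole population or arm, or those with non-missing data, as denominator.
- **Entry (Protocol 4.3, exclusion 15):** the bar is a Yes "answer on the C-SSRS ideation items 4 or 5" in the 3 months before Screening. Items 1-3 are not named.
- **Day -1 (Protocol Schedule of Events, footnote 16):** "C-SSRS not completed on Day -1 during Treatment Period 1". It is done on Day -1 of Period 2, which Protocol 5.1.2 confirms.

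Section 11.6 also refers to an external scoring guide for its methods and promises a listing of all results.

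**The concern.** A baseline that is collected and labelled but never used leaves the tables unable to answer the usual safety question: did anyone become suicidal, or more so, on treatment? A subject who reports a wish to be dead at Screening and again on Day 7 is counted in the same way as one who first reports it on Day 7.

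The crossover adds a second gap. The endpoint is a comparison of active treatment with placebo, yet 11.6 does not say which treatment or period a result belongs to. Ideation that begins in Period 1 and continues could be counted again in Period 2.

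The third matter is separate. A scale on which nothing was answered receives the same value as a negative one. At stake is the clarity of a small safety display, not the study's main conclusions.

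**Working it through.** The documents state no C-SSRS rate or event count, and the sample size of about 60 is not derived from a formula, so there is no plan figure to reproduce.

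**Step 1: apply the 11.6 ideation rule to three records.**
- Item 1 Yes at entry and again after dosing: indicator = 1, so the subject is counted.
- All five items No: indicator = 0.
- All five items missing: indicator = 0.

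Persisting entry ideation is therefore counted, and an unanswered scale cannot be told from a negative one.

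**Step 2: look for any use of baseline.** The overall count and the three composite tables are all conditioned only on time (after first dose, or treatment through follow-up). Section 11.6 has no new-or-worse condition, shift table or baseline row.

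**Step 3: look for assignment to treatment and period.** SAP 11.1 has an explicit rule for adverse events, including those in the washout. Section 11.6 has none. The SAP 6.1 default for categorical data is by disease type, treatment sequence and overall, which does not set active treatment against placebo. SAP 7.1 gives each period its own treatment start date, and 7.3 takes the last value before treatment start as baseline. Together these would make Day -1 the Period 2 baseline, but 11.6 labels Screening instead.

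**Step 4: compare the visit lists.**

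| Source | Period 2 Day -1 | Day 1 |
|---|---|---|
| Protocol Schedule of Events | yes | no |
| SAP Appendix 2 | yes | yes |
| SAP 11.6 text | no | no |

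**Step 5: illustrate the size.** Assumptions: N = 60; a proportion b enters with item 1-3 ideation, all of it persisting; 3% of the others develop new ideation; no missing scales.

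- Expected count under 11.6 = 60 × [b + 0.03 × (1 − b)]
- Pre-existing cases in that count = 60 × b
- Chance of at least one pre-existing case = 1 − (1 − b)^60

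| b (assumed) | Count under 11.6 | Rate | Pre-existing | Chance of at least one |
|---|---|---|---|---|
| 2% | 1.20 + 1.76 = 2.96 | 4.9% | 1.2 | 0.70 |
| 5% | 3.00 + 1.71 = 4.71 | 7.9% | 3.0 | 0.95 |
| 10% | 6.00 + 1.62 = 7.62 | 12.7% | 6.0 | above 0.99 |

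The new-onset rate among subjects without entry ideation is 3.0% in every row.

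**Step 6: missing scales.** If 10% of subjects (assumed) had no post-dose scale and were coded 0 with all 60 as denominator, the three rates would be multiplied by 0.9, giving 4.4%, 7.1% and 11.4%. In small counts, 3 cases with 6 unassessed subjects read 3/60 = 5.0% instead of 3/54 = 5.6%. This effect lowers the rate, whereas the missing baseline condition raises the count.

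**The case against.** The strongest reply is that nothing in 11.6 is false. It tabulates ideation endorsed on treatment, which is a legitimate descriptive display, and it already exceeds the listing planned in Protocol 8.10. A reader might infer that the SAP reports entry ideation as having arisen on study. The text does not support that: it never calls the events new or emergent, and it counts only what is endorsed again after dosing. What remains is that the tables cannot make the distinction. The listing lets a reader check single subjects but does not repair the percentages.

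Several further points limit the concern:
- **Crossover.** Stable ideation should appear under both treatments, so by itself it creates no treatment difference. It would be too strong to say that the tables cannot inform on drug effect. The absence of an assignment rule remains a gap.
- **Missing data.** Coding missing as 0 cannot make entry ideation look as if it arose on study; it only hides cases. SAP 7.4 and the non-missing denominator in 6.1 permit a milder reading of the rule. The C-SSRS is also a required Early Withdrawal assessment (Protocol 5.1.5) and is repeated at End of Study (5.1.6), visits that Protocol 4.6.2 plans for dosed subjects who leave. Many wholly unassessed subjects are unlikely.
- **Period 2 Day -1.** A reader might infer that a Yes there is counted as an event because it follows the first dose of the study. The 11.6 visit list omits that visit, so the documents do not settle whether it is counted.
- **Entry.** Exclusions 4, 7 and 19 may remove some subjects with item 1-3 ideation.
- **External guide.** It may contain baseline or missing-data rules. That cannot be checked from the documents, and the rules that 11.6 does write out include none.

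**Conclusion.** The point holds in a limited form and is of low severity. As written, the 11.6 tables mix persisting item 1-3 ideation with new or worsened ideation, and no stated rule ties a C-SSRS result to a treatment or period. With as few as 2% of 60 subjects carrying such ideation throughout, the chance of at least one pre-existing case in the count is 0.70. That figure, and every other rate used here, rests on assumed prevalence, full persistence and independent subjects.

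The coding of an unanswered scale as 0 is a separate fault, in tension with SAP 7.4. Its effect is probably small: 0.6 percentage points in the example with three cases, which itself assumes 6 of 60 subjects without any post-dose scale.

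**What to change.** In SAP 11.6:

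1. Keep the any-event tables. Add, by treatment, a tabulation of new or worsened ideation or behavior (or a shift table) against that period's pre-dose scale: Screening for Period 1 and Day -1 for Period 2.
2. Add Period 2 Day -1 to the visit list, and state that it is the Period 2 baseline and not a Period 2 event.
3. State how each C-SSRS result is assigned to treatment and period.
4. Reconcile the Day 1 C-SSRS marked in SAP Appendix 2 with the protocol schedule, which has none.
5. Set the indicators to missing when no item is answered. Use subjects with at least one post-dose C-SSRS in that period as the denominator.

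The Screening and Period 2 Day -1 assessments are already scheduled, so no new data are needed. The cost is SAP wording, one more derived flag and one more table.
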